## LIST OF ABBREVIATIONS

AE	adverse event
ALT	alanine aminotransferase (also SGPT)
APRI	AST:platelet ratio index
APTT	activated partial thromboplastin time
AST	aspartate aminotransferase (also SGOT)
BPM	beats per minute
CI	confidence interval
CMH	Cochran-Mantel-Haenszel
CSR	clinical study report
DAA	direct acting antiviral
DMC	Data Monitoring Committee
ECG	electrocardiogram
eCRF	electronic case report form
EOT	end of treatment
FAS	full analysis set
FDC	fixed-dose combination
FU	follow-up
GT	genotype
HCV	hepatitis C virus
HLGT	high level group term
HLT	high level term
INR	international normalized ratio of prothrombin time
IWRS	interactive web response system
LLOQ	lower limit of quantitation
LLT	lower level term
MedDRA	Medical Dictionary for Regulatory Activities
MELD	Model for End-Stage Liver Disease
Peg-IFN	pegylated interferon
PK	pharmacokinetics
PT	preferred term
Q1	first quartile
Q3	third quartile
RNA	ribonucleic acid
SAE	serious adverse event
SAP	statistical analysis plan
SD	standard deviation
SOC	system organ class
SOF	sofosbuvir (Sovaldi ® )

SVR	sustained virologic response
SVRx	sustained virologic response x weeks after stopping study drug
TE	treatment-emergent
TFLs	tables, figures, and listings
TND	target not detected
ULN	upper limit of normal
VEL	Velpatasvir
VF	virologic failure
WHO	World Health Organization

## 1. INTRODUCTION

This statistical analysis plan (SAP) describes the statistical analysis methods and data presentations to be used in tables, figures, and listings (TFLs) in the clinical study report (CSR) for Study GS-US-342-1522. This SAP is based on the original study protocol dated 17 July 2015 and the electronic case report form (eCRF). The SAP will be finalized prior to database finalization. Any changes made after the finalization of the SAP will be documented in the CSR.

### 1.1. Study Objectives

The primary objectives of this study are:

- To evaluate the efficacy of treatment with sofosbuvir (SOF)/velpatasvir (VEL, GS-5816) fixed dose combination (FDC) for 12 weeks in subjects with chronic HCV infection as measured by the proportion of subjects with sustained viral response 12 weeks after cessation of treatment (SVR12)
- To evaluate the safety and tolerability of treatment with SOF/VEL for 12 weeks

The secondary objectives of this study are:

- To determine the proportion of subjects who attain SVR at 4 and 24 weeks after cessation of treatment (SVR4 and SVR24)
- To evaluate the kinetics of circulating HCV RNA during treatment and after cessation of treatment
- To evaluate the emergence of viral resistance to SOF and VEL during treatment and after cessation of treatment

The exploratory objectives of this study are:

PPD [REDACTED]

[REDACTED]

### 1.2. Study Design

This is a multi-center, open-label study of adult subjects with chronic HCV that will evaluate the safety, tolerability and antiviral efficacy of SOF/VEL FDC for 12 weeks in subjects with chronic HCV infection.

Approximately 120 subjects will be enrolled to receive: SOF/VEL (400 mg/100 mg) once daily for 12 weeks.

Up to 20% of subjects enrolled in the study may have cirrhosis at baseline and up to approximately 20% may be treatment-experienced.

The total time to complete all study visits is approximately 40 weeks including:

- 28 day (4 weeks) screening period (or can be extended to 42 days)
- 12 week treatment period
- Up to 24 week posttreatment period

The schedule of assessments is provided as an appendix to the SAP (Appendix 1).

### 1.3. Sample Size and Power

With a sample size of 120, the 95% exact confidence interval for different observed SVR12 rates are presented below:

Observed SVR12 rate	2-sided 95% exact CI
80% (96 out of 120)	72% - 87%
85% (102 out of 120)	77% - 91%
95% (114 out of 120)	89% - 98%

## **2. TYPE OF PLANNED ANALYSIS**

### **2.1. Primary Efficacy Endpoint Analysis**

The primary efficacy endpoint analysis (for SVR12) will be conducted when all subjects have completed the 12 week posttreatment visit or have prematurely discontinued from study. All the safety and efficacy data through the Posttreatment Week 12 visit will be finalized and included for the analysis.

### **2.2. Final Analysis**

The final analysis will be conducted when all subjects have completed the 24 week post treatment visit or prematurely discontinued from the study. The data will be finalized after all data queries are resolved for study visits through completion of the 24-week posttreatment visit. At the conclusion of data finalization, the study statistician and statistical programmers will run the final version TFLs.

### **3. GENERAL CONSIDERATIONS FOR DATA ANALYSES**

Analysis results will be presented using descriptive statistics. For categorical variables, the number and percentage of subjects in each category will be presented; for continuous variables, the number of subjects (n), mean, standard deviation (SD) or standard error (SE), median, first quartile (Q1), third quartile (Q3), minimum, and maximum will be presented.

Data collected in the study will be presented in by-subject listings for all subjects in the Safety Analysis Set, unless otherwise specified. All by-subject listings will be presented by subject identification (ID) number in ascending order, unless otherwise specified.

#### **3.1. Analysis Sets**

Analysis sets define the subjects to be included in an analysis. Analysis sets and their definitions are provided in this section. The number of subjects eligible for each analysis set will be provided. Subjects who were excluded from each analysis set will be summarized or provided in a by-subject listing by genotype.

##### **3.1.1. All Enrolled Analysis Set**

All Enrolled Analysis Set includes all subjects enrolled in the study after screening. Subjects are grouped within the All Enrolled Analysis Set by genotype.

##### **3.1.2. Full Analysis Set**

The Full Analysis Set (FAS) includes subjects who are enrolled into the study and received at least 1 dose of study drug. The study drugs in this study are SOF/VEL. Subjects are grouped within the FAS by genotype.

This is the primary analysis set for efficacy analyses.

##### **3.1.3. Safety Analysis Set**

The Safety Analysis Set includes all subjects who received at least 1 dose of study drug. This is the primary analysis set for safety analyses.

#### **3.2. Subject Grouping**

For analyses based on the All Enrolled Analysis Set or FAS, subjects will be grouped according to the genotype (1a, 1b, 1 total and 3).

#### **3.3. Examination of Subject Subsets**

Subject subsets within each genotype will also be explored for the primary efficacy endpoint, SVR12. The baseline characteristics include the following:

- age (< 65 years, ≥ 65 years)

- sex (male, female)
- cirrhosis (presence, absence) for subjects
- prior HCV treatment experience (treatment naive, treatment experienced)
- prior HCV treatment for treatment experienced subjects (direct acting antiviral [DAA] + pegylated interferon [Peg-IFN] + RBV, Peg-IFN + RBV, Other)
- prior HCV treatment response (nonresponse, relapse/breakthrough) for treatment experienced subjects
- HCV genotype
- baseline HCV RNA ( $< 800,000$  IU/mL,  $\geq 800,000$  IU/mL)
- baseline body mass index (BMI) ( $< 30$  kg/m^2,  $\geq 30$  kg/m^2)
- baseline alanine aminotransferase (ALT) ( $\leq 1.5 \times$  upper limit of normal (ULN),  $> 1.5 \times$  ULN)
- IL28B (CC, non-CC; with non-CC further broken down to CT, TT)
- adherence to study regimen ( $< 80\%$ ,  $\geq 80\%$ )

### **3.4. Missing Data and Outliers**

#### **3.4.1. Missing Data**

In general, missing data will not be imputed unless methods for handling missing data are specified.

For missing last dosing date of study drug, imputation rules are described in Section 3.6.1. The handling of missing or incomplete dates for adverse event (AE) onset is described in Section 7.1.5.2, and for prior and concomitant medications in Section 7.4

For analyses of categorical HCV RNA data, missing posttreatment HCV RNA data will have the missing data imputed. Missing on-treatment HCV RNA will have missing data imputed up to the time of the last dose (for on-treatment displays). If the study day associated with the last dosing date of any study drug is greater than or equal to the lower bound of a visit window, and the value at the visit is missing, then the value will be imputed. If the study day associated with the last dosing date is less than the lower bound of a visit window then the on-treatment value at that visit will remain missing.

If a HCV RNA data point is missing and is preceded and followed in time by values that are “ $<$  lower limit of quantification (LLOQ) target not detected (TND),” then the missing data point

will be set to “< LLOQ TND.” If a data point is missing and preceded and followed by values that are “< LLOQ detected,” or preceded by “< LLOQ detected” and followed by “< LLOQ TND,” or preceded by “< LLOQ TND” and followed by “< LLOQ detected,” then the missing value will be set to “< LLOQ detected.” In these situations the data point will be termed a bracketed success; otherwise, the data point will be termed a bracketed failure (ie,  $\geq$  LLOQ detected). If a data point is missing and is not bracketed, the missing data point will also be termed a failure (ie,  $\geq$  LLOQ detected) except for SVR24, which will be imputed according to SVR12 status. Success for SVR12 who have no further HCV RNA measurements collected will be counted as a success for SVR24 due to the high correlation between these 2 endpoints.

For the analyses of continuous HCV RNA efficacy data, when and only when a missing HCV RNA value is imputed as < LLOQ TND or < LLOQ detected according to the imputation rule described above, the corresponding continuous value will be imputed to LLOQ – 1 IU/mL. No other imputation will be performed for continuous HCV RNA data.

For health-related quality of life data SF-36, missing data will not be imputed.

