## 4. SUBJECT DISPOSITION

### 4.1. Subject Enrollment and Disposition

A summary of subject enrollment will be provided for each country and investigator. The summary will present the number and percentage of subjects in the Safety Analysis Set. For each column, the denominator for the percentage calculation will be the total number of subjects analyzed for that column.

A summary of subject disposition will be provided by genotype and overall. This summary will present the number of subjects screened, the number of subjects not enrolled, the number of subjects enrolled, the number of subjects enrolled but never treated, the number of subjects enrolled and treated (ie, safety analysis set), in FAS, and the number and percentage of subjects in each of the categories listed below. The denominator for the percentage calculation will be the total number of subjects in the Safety Analysis Set for each column.

- Continuing study treatment (if applicable)
- Completed study treatment
- Did not complete study treatment with reasons for premature discontinuation of study treatment
- Completed study
- Did not complete the study with reasons for premature discontinuation of study

Among subjects who completed study treatment and who discontinued study treatment, the number and percentage of subjects will be summarized for:

- Who had no HCV posttreatment Week 4 assessment and thereafter (No HCV FU-4 Assessment and thereafter)
- Who had HCV posttreatment Week 4 assessment but no HCV posttreatment Week 12 and thereafter (With HCV FU-4 but No FU-12 and thereafter)

If a subject did not have any HCV RNA assessment  $\geq 21$  days after the last dose of any study drug (ie, lower bound of FU-4 visit for HCV RNA data), the subject is categorized as having “No HCV FU-4 and thereafter.” If a subject had the HCV FU-4 assessment but did not have any HCV RNA assessment  $\geq 70$  days after the last dose of any study drug (ie, lower bound of FU-12 visit for HCV RNA data), the subject is categorized as having “With HCV FU-4 but No FU-12 and thereafter.”

In addition, the total number of subjects who were enrolled, and the number of subjects in each of the disposition categories listed above will be depicted by a flowchart.

The following by-subject listings will be provided by subject ID number in ascending order to support the above summary tables:

- Disposition for subjects who complete study treatment and study

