### 6.2.2. Analysis Methods for Secondary Efficacy Endpoints

For analyses of HCV RNA  $<$  LLOQ by visit while on treatment and during the posttreatment (SVR) follow-up period, subjects will be assigned a value at each visit based on the analysis visit windows specified in Section 3.6.2. Missing values will be imputed based on the categorical imputation rules described in Section 3.4.1. The 2-sided 95% exact CI based on Clopper-Pearson method will be provided for the percentage of subjects with HCV RNA  $<$  LLOQ at each visit within each genotype. The overall category for “HCV RNA  $<$  LLOQ” will be split into the following 2 subcategories: “ $<$  LLOQ TND” for subjects with target not detected and “ $<$  LLOQ detected” for subjects with  $<$  LLOQ in tabular displays.

Graphs for the percentage of subjects with HCV RNA  $<$  LLOQ over time during treatment will be displayed by genotype.

Summary statistics will be presented for absolute values and change from baseline in HCV RNA ( $\log_{10}$  IU/mL), by genotype and overall and by visit through EOT. Imputation rules described in Section 3.4.1 will be used to assign HCV RNA values for missing values at a visit that are bracketed by “ $<$  LLOQ TND” and/or “ $<$  LLOQ detected”. Otherwise, a missing = excluded analysis will be performed. Plots of the mean  $\pm$  SD and median (Q1, Q3) of absolute values and changes from baseline in HCV RNA through EOT will be presented.

For the SVR12 endpoint analysis, a summary table of the number and percentage of subjects with SVR12, virologic failure, and Other by genotype will be created. All subjects who achieve SVR12 will be categorized as SVR12. Virologic failure will be descriptively summarized as “on-treatment virologic failure” and relapse (which will be broken down by study drug completed yes/no). Subjects who do not achieve SVR12 and do not meet criteria for virologic failure will be categorized as “Other.” The denominator for relapse will be the number of subjects who had HCV RNA  $<$  LLOQ on their last observed on-treatment HCV RNA measurement; otherwise, the denominator will be the number of subjects in the FAS.

A concordance table between SVR12 and SVR24 will be provided for each genotype. Subjects with both observed SVR12 and observed SVR24 data will be included for this analysis.

Drug resistant substitutions will be analyzed and reported based on change from baseline sequence and/or change from HCV genotype reference strain.

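### Does carrying SVR12 success forward to SVR24 for responders with no later HCV RNA make the SVR24 rate and its exact CI misleading?

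*SAP*

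**What the plan says.** SAP Section 3.4.1 treats a missing HCV RNA value that is not bracketed by values below LLOQ as a failure, "except for SVR24, which will be imputed according to SVR12 status". It then spells out the favourable half of the exception: "Success for SVR12 who have no further HCV RNA measurements collected will be counted as a success for SVR24 due to the high correlation" between the two endpoints.

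Section 6.2.2 carries this into the by-visit and SVR analyses: "Missing values will be imputed based on the categorical imputation rules described in Section 3.4.1". The interval follows: "The 2-sided 95% exact CI based on Clopper-Pearson method will be provided for the percentage of subjects with HCV RNA" below LLOQ at each visit, within each genotype.

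The same section plans a check on measured data only: "A concordance table between SVR12 and SVR24 will be provided for each genotype", and "Subjects with both observed SVR12 and observed SVR24 data will be included for this analysis".

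Section 2.2 allows for subjects who leave early: "The final analysis will be conducted when all subjects have completed the 24 week post treatment visit or prematurely discontinued from the study". In Section 4.1 the last category for missing HCV RNA follow-up is "Who had HCV posttreatment Week 4 assessment but no HCV posttreatment Week 12 and thereafter"; there is no matching category for FU-24. Section 4.1 does plan the number and percentage who did not complete the study, with reasons and a listing. Section 3 provides by-subject listings of collected data for the Safety Analysis Set unless otherwise specified.

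**The concern.** SVR24 is the only posttreatment endpoint in this SAP for which an unbracketed missing value can become a success. Carried-forward responders enter the exact interval as if they had been measured. For a given number of observed late failures, neither the estimate nor the interval shows how many responders missed FU-24. Among those responders the rule can err only upward, because a relapse after SVR12 in a subject who never returns is scored as a success.

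No planned table row gives the number carried forward, and the disposition summary does not supply it. If many responders missed FU-24, the reported SVR24 would largely restate SVR12, and a reader looking for evidence of durable response could take it for independent confirmation.

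**Working it through.** **Inputs.** N = 120 (SAP 1.2); the example 114/120 (SAP 1.3); two-sided 95% Clopper-Pearson intervals (SAP 6.2.2). The SAP gives no number of responders without FU-24 data (m), no proportion of them relapsing late (r) and no genotype sizes. So m and r are assumed, and the figures are pooled over 120.

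**Step 1: the SAP's own figures.** Clopper-Pearson gives 71.7-86.8 for 96/120, 77.3-90.9 for 102/120 and 89.4-98.1 for 114/120. All three agree with Section 1.3 after rounding.

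**Step 2: behaviour of the rule.** With no observed late relapse, SVR24 is 114/120 = 95.0% (89.4-98.1) for m = 0, 6, 12, 24 or 36. It is not fixed in general: two observed late relapses give 112/120 = 93.3% (87.3-97.1).

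**Step 3: possible upward error.** Expected error = m × r / 120.

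| m | r = 2% | r = 5% | r = 10% |
|---|---|---|---|
| 11 | 0.2 points | 0.5 points | 0.9 points |
| 36 | 0.6 points | 1.5 points | 3.0 points |

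One full point needs m × r = 1.2 unseen relapses. Within a genotype, the same formula applies with that group's m and denominator.

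**Step 4: what the concordance table shows.** The relevant part is its row of observed SVR12 successes: of those measured at both visits, how many kept their response. If all 114 SVR12 successes were observed and m = 11, the row holds 114 − 11 = 103 subjects. Let d be the number of them with an observed late relapse. If the 11 unmeasured responders behaved like the 103 measured ones, SVR24 would be 114/120 × (103 − d)/103. The planned figure is (114 − d)/120.

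| d | Planned | Missed responders behave like measured ones |
|---|---|---|
| 0 | 95.0% | 95.0% |
| 1 | 113/120 = 94.2% | 0.95 × 102/103 = 94.1% |
| 2 | 112/120 = 93.3% | 0.95 × 101/103 = 93.2% |

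The two agree exactly when d = 0 and differ by about 0.1 point per observed relapse (0.95/103 − 1/120 = 0.0009). If late relapse were common enough to undermine the rule, this row would normally show it.

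**Step 5: would another rate be better?**

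- Leaving out only the carried-forward subjects gives (114 − m)/(120 − m): 103/109 = 94.5% (88.4-98.0) at m = 11 and 78/84 = 92.9% (85.1-97.3) at m = 36. These falls occur with no late relapse at all. Successes are removed while every SVR12 failure stays, including any without FU-24 data. The drop comes from the denominator and says nothing about durability.
- Counting missing as failure gives 103/120 = 85.8% (78.3-91.5) at m = 11. That assumes all 11 relapsed, so it is only a worst-case bound.

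**The case for a change.** The strongest case on the other side is about visibility. The SAP gives no figure for the correlation it relies on, plans no interval for the concordance table, and names no row for carried-forward successes. All of that is true.

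Two further arguments are weaker.

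- *The concordance table's SVR24 margin can exceed the full analysis set rate.* With m = 11 and 4 of the 6 SVR12 failures lacking FU-24 data, the margin is 103/105 = 98.1%. The SAP does not propose that margin as an SVR24 rate. SVR12 failures never enter the row that tests whether responders keep their response.
- *Subtracting that row from the SVR12 successes gives only an approximate count.* A subject without FU-12 data but below LLOQ at FU-4 and FU-24 is a bracketed SVR12 success and is absent from the table. Two such subjects would make the difference 13 instead of 11. This is correct, but such a subject must have no sample in the whole FU-12 window of days 70 to 146 (77 days) and then return. The by-subject listings allow an exact count among about 120 subjects.

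The rule is also not purely favourable. A subject below LLOQ at FU-4 with no later data is an SVR12 failure and takes that status at SVR24.

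What stands is that a carried-forward count and an FU-24 disposition category would be convenient for the reader.

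**Conclusion.** The concern does not hold. The SAP states the rule openly, confines it to SVR12 successes without later HCV RNA, gives its reason, and plans an observed-only table that tests that reason. Nothing in Sections 3.4.1, 6.2.2, 4.1 or 2.2 conflicts, and no figure is wrong.

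In the pooled 114/120 example with 11 carried forward, the expected upward error is 0.2 to 0.9 points for unseen relapse of 2% to 10%. It reaches 3.0 points only at the extreme shown, with 36 of 114 responders unmeasured and 10% of them relapsing. These are assumed inputs, and a small genotype group with many missed visits could see a larger shift. The one thing the data cannot settle is whether missed responders relapse more often than measured ones, and neither alternative rate resolves that.

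SVR24 is a secondary, descriptive endpoint and SVR12 does not depend on this rule. Following the plan as written leads to a sound conclusion; additional rows would be a matter of presentation.

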### **3.4.2. Outliers**

Outliers will be identified during data management and data analysis process, but no sensitivity analyses will be conducted. All data will be included in the data analysis.

### **3.5. Data Handling Conventions and Transformations**

By-subject listings will be presented for all subjects in the Safety Analysis Set and sorted by subject ID number, visit date, and time (if applicable) unless otherwise specified. Data collected on log forms, such as AEs, will be presented in chronological order within subject.

Age (in years) on the date of the first dose of study drug and sex at birth will be used for analyses and presentation in listings.

If a subject was not dosed with study drug at all, then the date the informed consent was signed will be used instead of the first dose date of study drug.

Non-pharmacokinetic (PK) data that are continuous in nature but are less than the lower limit of quantitation or above the upper limit of quantitation will be imputed as follows:

- A value that is one unit less than the limit of quantitation will be used for calculation of descriptive statistics if the datum is reported in the form of “< x” (where x is considered the limit of quantitation). For example, if the values are reported as < 50 and < 5.0, values of 49 and 4.9, respectively, will be used for calculation of summary statistics. An exception for this rule is any value reported < 1. For the values reported as < 1 or < 0.1, value of 0.9 or 0.09 will be used for calculation of summary statistics.

- A value that is one unit above the limit of quantitation will be used for calculation of descriptive statistics if the datum is reported in the form of “> x” (where x is considered the limit of quantitation). Values with decimal points will follow the same logic as above.
- The limit of quantitation will be used for calculation of descriptive statistics if the datum is reported in the form of “≤ x” or “≥ x” (where x is considered the limit of quantitation).

COBAS® AmpliPrep/COBAS® TaqMan® HCV Quantitative Test, v2.0 will be used to determine HCV RNA results in this study. The lower limit of quantitation (LLOQ) of the assay is 15 IU/mL.

When the calculated HCV RNA value is within the linear range of the assay, then the result will be reported as the “<< numeric value>> IU/mL.” This result will be referred to in this document as the numeric result or as “≥ LLOQ detected” for categorical result.

When HCV RNA is not detected, the result is reported as “No HCV RNA detected” or “target not detected”. This result will be referred to in this document as “< LLOQ target not detected” or “< LLOQ TND.”

When the HCV RNA IU/mL is less than LLOQ of the assay, the result is reported as “< 15 IU/mL HCV RNA detected”. This result will be referred to in this document as “< LLOQ detected.”

The overall category of HCV RNA < LLOQ includes “< LLOQ TND” and “< LLOQ detected.”

For numerical HCV RNA data, values below LLOQ will be set to the LLOQ – 1 IU/mL (ie, 14 HCV RNA IU/mL). HCV RNA values returned as “No HCV RNA detected” will also be set to 14 IU/mL.

For selected analyses, HCV RNA data (IU/mL) will be transformed to the logarithmic (base 10) scale ( $\log_{10}$  IU/mL).

